2.8 Endpoints

2.8.1 Primary Endpoint

The primary endpoint is the catheter indwell time, defined as the time from catheter insertion to time of catheter failure. It is measured in hours.

2.8.2 Secondary Endpoints

- Haemolysis measured in three different ways with cfHb, AU480 and visual assessment: Quantification of cell free hemoglobin and frequency of samples exceeding a concentration of 50 mg/dL.
- Blood draw fill time. Defined as the duration from attachment of vacutainer to time when blood fills to pre-defined fill level. It is measured in seconds.
- Relationship, if any, between catheter blood draw patency indwell time and presence of intra/extravenous thrombi, catheter angle/tip location *in situ*, catheter length in vessel, vein depth from skin surface, C/V ratio, and vessel anatomy assessed via the incidence of:
 - Intravenous thrombus (mural, at tip)
 - Vein collapse
 - Presence and location of a valve relative to catheter tip
 - Side branches relative to catheter tip detected through ultrasound
- Evaluation of changes in vessel dimensions (Catheter to vein ratio), PIVC position (insertion angle and *in situ* tip position), and hemodynamics from baseline throughout indwell time evaluated using:
 - Vessel diameter or Catheter to vein ratio (C/V ratio)
 - Blood flow velocity
 - *In situ* tip position
 - Extravenous thrombus visually observed upon device removal within:
 - * Catheter hub
 - * Needleless connector
 - * Extension tubing via visual observation

2.8.3 Exploratory Endpoints

- Incidence of complications prompting device removal assessed by the frequency of occurrence of the following events:
 - Vein collapse
 - Phlebitis
 - Venous thrombosis
 - Dislodgement
 - Infiltration (called Extravasation in the protocol)
 - Accidental removal
- Manual flush variability will be evaluated using duration of flush and characteristics of Flush pressure profile (peak force) obtained on in-line pressure measurements

2.9 Acceptance Criteria

No acceptance criteria have been established for this study.

3 Intended Statistical Software and Data Information

The analysis will be conducted with R version 4.0.3 (2020-10-10) [1] or a more recent version. The extraction of the pressure profile and duration of flush characteristics will be performed by BDTI R&D

using LabView 2020 with the script PIVC linedraw, version 1.1.2. Results will be provided to the study statistician in a csv file.

4 Analysis Population Set(s)

4.1 Population Definitions

In the unforeseen circumstance of a protocol deviation (e.g., 20G PIVC instead of 22G PIVC; blood was collected into 6mL vacutainer before 2mL for a specific participant), the data will be analyzed “as treated” - that is, data will be analyzed as the participant’s actual received intervention. However, in the unforeseen circumstance of a protocol deviation whereby a participant receives the wrong intervention (e.g., two different gauge catheters; two 20G catheters of the same length), they will be treated as per protocol (PP) and thus their data will be excluded from the study because paired comparison of catheter length will not be possible.

5 Statistical Analysis/Calculations

5.1 Derived Variables

Below is a list of variables that require calculation or transformation of data that will be used for derived outcomes. Any variables that are not listed below do not have derived outcomes.

5.1.1 Haemolysis: Quantification and frequency of occurrence

To quantify cfHb, whole blood collected and anticoagulated with Ethylenediaminetetraacetic acid (EDTA), will be centrifuged at 1200 x g for 10 min. The top half of the supernatant will be added to 0.01% Na₂CO₃ (1:6) and the absorbance of each sample will be measured at 380, 415 and 450 nm using a spectrophotometer (MultiSkan GO, Thermo Fisher Scientific; MA, USA). The cfHb will subsequently be calculated from these absorbances using the Harboe method 45, as described in Equation 1.

$$\text{cfHb} \left(\frac{\text{mg}}{\text{dL}} \right) = \left(\frac{167.2\text{Abs}_{415} - 83.6\text{Abs}_{450} - 83.6\text{Abs}_{380}}{10} \right) \times \frac{1}{\text{dilution in Na}_2\text{CO}_3} \quad (1)$$

Additionally, an automated biochemistry analyzer (AU480, Beckman Coulter, USA) will be employed for a clinical measurement of haemolysis and assessing the frequency of cfHb above a threshold of 50 mg/dL. The accuracy of the device is not sensitive to measurements below 50 mg/dL. Lastly, visual assessment of haemolysis will be checked, and photographs taken of each sample.

5.1.2 Dominant arm

The identification of the dominant will be performed for each subject crossing information from the VENIPUNCTURE CRF questions “Arm Venipuncture Performed from?” and “Was this the Non-Dominant Arm?”, available in the variables DELOC and DENDARM, respectively, from the table VPVP.

5.1.3 Blood draw fill time

The blood draw fill time (seconds) will be calculated manually using a stopwatch - from connection to blood reaching predetermined fill line.

5.1.4 Intravenous thrombus

The presence of an intravenous thrombus (mural, at tip) will be ascertained using ultrasound.

5.1.5 Vessel diameter, Catheter to vein ratio

The vessel diameter, and C/V ratio (Catheter to vein ratio) will be derived from the mean average of three cross-sectional, B-mode scans to be taken with the indwelling PIVC in view. The vessel diameter

will be calculated from the horizontal axis using the internal calculations of the ultrasound. The data will be reported as the average of the values taken from three images. The catheter diameter will be derived from the device specifications, where catheter outer diameter is reported to be 0.90 mm and 1.10 mm, respectively for 22G and 20G catheters.

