6 STUDY INTERVENTIONS

6.1 Study Device

The BD Nexiva closed IV catheter systems are intended to be inserted into a patient's vascular system for short term use to sample blood, monitor blood pressure, or administer fluids. These devices may be used for any patient population with consideration given to adequacy of vascular anatomy, procedure being performed, fluids being infused, and duration of therapy.

BD Nexiva closed IV catheter systems are over-the-needle, intravascular (IV) catheters. These devices have a radiopaque BD Vialon catheter, needle, needle shield, septum, stabilization platform, integrated extension tubing, clamp, Luer adapter, and vent plug. The needle and catheter are protected by a needle cover

The closed system is designed to keep blood contained within the device throughout the insertion process. The septum is designed to wipe visible blood from the needle surface as the needle is withdrawn from the catheter, further reducing the risk of blood exposure. The needle tip is passively protected when the needle is removed, reducing the risk of accidental needlestick injury.

These devices have BD Instaflash™ Needle Technology, allowing for immediate visualization of blood along the catheter.

Continuous blood return is seen in the extension tubing. The vent plug prevents blood leakage from the extension tubing during insertion. Both the stabilization platform and Luer connector are color coded to

indicate catheter gauge size (24 GA (0.7 mm) = Yellow, 22 GA (0.9 mm) = Blue, 20 GA (1.1 mm) = Pink, 18 GA (1.3 mm) = Green).

See the IFU included in the Appendix (16.1) for full details on the device.

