7.4.3 Vessel diameter, C/V ratio

Calculation of the vessel diameter, and C/V ratio will be achieved via assessment of the three cross-sectional, B-mode scans to be taken with the indwelling tip PIVC in view. The vessel diameter and catheter diameter will be calculated from the horizontal axis using the internal calculations of the clinically approved ultrasound. The data will be reported as the average of the values taken from the three images.

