10.6 Secondary Endpoint(s)

Linear mixed-effects models will be used to evaluate the following endpoints over time and determine the effect on PIVC indwell time for a given configuration (i.e., length/gauge):

- 1) cfHb concentration;
- 2) blood draw fill time;
- 3) blood flow velocities above or below the catheter
- 4) vessel dimensions; and
- 5) intravenous thrombus size.

Underlying normality assumptions will be verified and if not fulfilled non-parametric tests will be used. Multivariate analysis (to be defined in the SAP) will be employed to assess the effect of baseline characteristics on catheter indwell time and thus identify their power as predictive biomarkers using the following the independent variables including, but not limited to:

- 1) angle of insertion;
- 2) vessel dimension;
- 3) presence of side branches and/or intravenous valves;
- 4) age;
- 5) sex;
- 6) height;
- 7) weight;
- 8) BMI;
- 9) medical history questionnaire responses; and
- 10) exploratory endpoints.

A multiple-logistic regression analysis will be employed to assess the effect of baseline characteristics on catheter failure over a period of 72 hours and thus identify their power as predictive biomarkers using the independent variables including, but not limited to:

- 1) angle of insertion;
- 2) vessel dimension;
- 3) presence of side branches and/or intravenous valves;
- 4) age;
- 5) sex;
- 6) height;
- 7) weight;
- 8) BMI;
- 9) medical history questionnaire responses; and
- 10) exploratory endpoints.

A chi squared analysis will be employed to assess the proportion of individuals in each group (i.e., PIVC length and gauge) that have presence of the following at failure/end-of-protocol:

- 1) vein collapse;
- 2) intravenous thrombus; and

3) extravenuous thrombus.

All data will be evaluated using statistical modeling software (Prism, Release 8.3; GraphPad Software Inc., USA) or R (R 3.6.2 or higher). P-values ≤ 0.05 will be considered statistically significant.

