Line plots will be similar to the example provided for cfHb in Figure B.3.2 and bar plots will be similar to the example provided for Haemolysis occurrence in Figure B.4.1, both represented in Appendix B.

Mixed effect models will be used with corresponding response and subject as random effect. Time, gauge, length, Vacutainer tube volume and baseline measurement of response will be fixed effects. Depending on the type of the response variable, the models will be:

- Linear: C/V ratio, catheter length, catheter insertion angles and blood flow velocity
- Logistic: Tip positions

Depending on model results, contrast based multiple comparisons will be used to compare means between conditions (between gauge, between length) at each timepoint. Results will be provided in Tables similar to the example given for Blood Draw Fill time in Tables A.9.3 and A.9.4, as can be found in the Appendix A.

The relationship between C/V ratio and Blood Draw Time as well as between C/V ratio and Blood Flow Velocity will be investigate using relevant graphical representation (scatter plots) and measure of association.

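### SAP 5.2.2.4 models C/V ratio as its only vessel-dimension response, so its gauge comparison cannot show whether the veins responded differently

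*SAP*

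**What the plan says.** Both documents set an objective of evaluating change in vessel dimensions from baseline through the indwell period (Protocol 3.1, SAP 1.2.2). Protocol 3.1 gives vessel diameter as the endpoint, and Protocol 10.6 lists vessel dimensions among the responses for linear mixed-effects models.

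SAP 2.8.2 leaves the measure open: "Vessel diameter or Catheter to vein ratio (C/V ratio"). SAP 5.2.2.4 then settles it. Its list of characteristics to evaluate contains C/V but not vessel diameter, and so does its list of modelled responses: "Linear: C/V ratio, catheter length, catheter insertion angles and blood flow velocity". Gauge, length, time and the baseline of the response are fixed effects. Depending on the model results, gauges are contrasted at each time point.

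The two documents derive the numerator differently. SAP 5.1.5 takes it from the specification: "The catheter diameter will be derived from the device specifications, where catheter outer diameter is reported to be 0.90 mm and 1.10 mm", for 22G and 20G in that order. Protocol 7.4.3 measures it on the scan: "The vessel diameter and catheter diameter will be calculated from the horizontal axis using the internal calculations of the clinically approved ultrasound".

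SAP 5.1.5 also defines C/V from scans with the catheter in view, whereas Table 2.7.1 schedules a C/V at D1.1, before insertion.

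**The concern.** C/V is catheter diameter divided by vein diameter. Gauge is randomised between participants, so the numerator differs between the two gauge groups by design. Veins that behave identically give different C/V values, and different C/V changes in points, in the two groups. A gauge contrast or gauge-by-time term on C/V mixes the catheter's own size with any response of the vein, and the objective asks about the vein. At stake is the gauge part of one secondary objective: the response the protocol planned to model is not in the SAP's model list, and its replacement cannot answer the question alone.

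**Working it through.** **Inputs from the documents.** Catheter outer diameter d is 0.90 mm (22G) and 1.10 mm (20G) in SAP 5.1.5. Protocol 6.1 agrees: "22 GA (0.9 mm) = Blue, 20 GA (1.1 mm) = Pink". The minimum vein diameter is about 2.55 mm for both gauges, with a C/V limit of 45% (Protocol 5.1 and 5.2). There are 20 participants per gauge (Protocol 4.1).

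**Assumed.** The documents give no expected vein change and no measurement error, so ranges are shown.

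**Plan's own figure.** The plan states no size for this effect. The nearest check is eligibility: 1.10/2.55 = 43.1%, which is under 45%, so the diameters fit the entry rule.

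**Step 1, level.** C/V = d/V, so the 20G to 22G ratio is 1.10/0.90 = 1.222 for any vein diameter V.

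| V (mm) | 20G | 22G |
|---|---|---|
| 2.55 | 43.1% | 35.3% |
| 3.0 | 36.7% | 30.0% |
| 4.0 | 27.5% | 22.5% |

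**Step 2, change.** If every vein goes from V to fV, the C/V change is (d/V)(1/f − 1). The gauge gap is (0.20/V)(1/f − 1). With V = 3.0 mm assumed:

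| Vein change | 20G (points) | 22G (points) | Size of gap (points) |
|---|---|---|---|
| none | 0 | 0 | 0 |
| +10% | −3.33 | −2.73 | 0.61 |
| +20% | −6.11 | −5.00 | 1.11 |
| −10% | +4.07 | +3.33 | 0.74 |

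**Step 3, baseline covariate.** With the same d at baseline, later C/V equals baseline C/V divided by f. For +10%, 36.67/1.1 = 33.33 and 30.00/1.1 = 27.27. A baseline slope of 1/1.1 = 0.909 therefore leaves no gauge difference at that time. Measurement error in the baseline flattens the slope and lets part of the shift back in. Because f can differ by time, full removal also needs a baseline-by-time term.

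**Step 4, simulation with no gauge effect on the vein.** 3000 runs; 20 participants per gauge, two arms each, seven times. Assumed: vein mean 3.3 mm, SD 0.5, truncated at 2.55 mm; measurement CV 3% or 10%; participant slope SD 3%, with 10% as a check; vein change over 72 hours from −15% to +30%. Least squares on each participant's mean and slope stood in for the mixed model. False-positive rates at a nominal 5% for C/V:

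- Gauge, no baseline covariate: 99% (shift 5.4 to 6.6 points).
- Gauge, with baseline C/V: 6–8% at 3% CV (about 0.15 points); 27–37% at 10% CV (1.2 to 1.45 points).
- Gauge-by-time, no baseline-by-time term: 5% if veins do not change. For 3% / 10% CV: 31% / 10% at +10% and 70% / 24% at +20%. At +20% with slope SD 10%: 20% / 15%.
- Gauge-by-time, with a baseline-by-time term: 4–6%.

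On log C/V, gauge-by-time is 4.6–6.0%, but the constant log(1.10/0.90) = 0.20 stays in the response. With vessel diameter in mm, the rates are 4.5–5.4% for gauge and 4.7–5.8% for gauge-by-time in every scenario.

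**The case against.** A reader might infer that the fixed nominal diameter is the fault, and that the planned estimates carry a 22% gauge difference and a false gauge-by-time effect. The documents do not support either reading.

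- **Cause.** A 20G catheter is wider than a 22G. Measuring it on the scan, as Protocol 7.4.3 says, would give about the same ratio. The nominal value is also a sensible choice at D1.1, where there is no catheter to measure.
- **The 22%.** It describes the raw ratio. SAP 5.2.2.4 already adjusts for the baseline of the response, and Step 3 shows that this takes out most of the constant shift. The 27–37% result needs an assumed 10% measurement CV.
- **Gauge-by-time.** Section 5.2.2.4 names no such term, and the contrasts are conditional. The gap is zero if veins do not change. The general rule in SAP 5.2.4 initially admits two-way interactions, which would include baseline-by-time, and allows transformation.
- **C/V has its own interest.** It appears in the objectives and the eligibility criteria, and a higher C/V with 20G is a fact about the device.
- **Vessel diameter is still present.** SAP 5.1.5 derives it, and SAP 2.8.2 names it as an alternative.

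All of this stands, and it narrows the point. Three things remain. The section that specifies the models omits vessel diameter. The baseline adjustment works as described only if D1.1 C/V uses the nominal diameter, which is not stated. The other safeguards depend on the data: SAP 5.2.4 drops interactions that are not significant and considers transformation only when assumptions fail.

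**Conclusion.** The point holds in a limited form. As SAP 5.2.2.4 is written, a gauge result on C/V cannot be read as a difference in vein response, and the response planned in Protocol 10.6 is not modelled. The 22% difference in raw C/V is exact and follows from the two stated diameters. What survives baseline adjustment rests on assumptions: about 0.15 points at 3% measurement CV and 1.2 to 1.45 points at 10%. The gauge-by-time gap is also conditional, running from 0 to about 1.1 points for vein widening of 0 to 20% at an assumed 3.0 mm. It would be wrong to say that a false gauge effect is certain.

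The consequence is small. Both catheters in a participant share a gauge, so the paired length comparison has no built-in numerator difference. The primary endpoint is untouched, and this is a secondary endpoint in a feasibility study without acceptance criteria (SAP 2.9). It is an inexpensive improvement to the plan.

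**What to change.** - In SAP 5.2.2.4, add vessel diameter (mm) to the evaluated characteristics and as the modelled response for the vessel-dimension objective, with D1.1 vessel diameter as the baseline covariate.
- Keep C/V as a descriptive variable and a predictor. If it is still modelled, use log C/V and state that its gauge effect includes the catheter's own size.
- State how baseline C/V is derived at D1.1.
- Reconcile Protocol 7.4.3 (catheter diameter measured on the scan) with SAP 5.1.5 (diameter from the specification).

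The cost is wording, mainly in the SAP. No new data are needed: SAP 5.1.5 already derives vessel diameter, and SAP 2.7 already counts it among the data collected at 15 time points, which include D1.1.

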5.1.6 Blood flow velocity

The blood flow velocity calculations (i.e. maximum and mean velocity of 5 seconds of data) will be derived from the area underneath the velocity spectrum boundary using the internal measurement tool of the ultrasound.

5.1.7 Flush pressure profile and duration of flush

The flush pressure profile (i.e. duration and peak pressure) will be derived from the pressure trace from a 3 to 10 mL saline flush performed upon first accessing the device at each time point indicated in Table 2.7.1. Pressure (P) will be recorded prior to commencement of the flush and this will be defined as “baseline” pressure. Commencement of the flush will induce a spike in positive pressure, and this will be defined as “time point zero” (t_0). The time point at which the spike in positive pressure returns to baseline will indicate completion of the flush and will be defined as the “completion time point” (t_c). Subsequently, the duration of the flush will be derived by subtracting time point zero from the completion time point, as described in Equation 2.

$$\text{flush duration} = t_c - t_0 \quad (2)$$

Alternatively, the duration of the flush could be reduced to the time between the max pressure and the completion time point, as described in Equation 3.

$$\text{alternative flush duration} = t_{max} - t_0 \quad (3)$$

The pressure reading with the maximal value between the two time points will be recorded as the peak pressure, defined as in Equation 4.

$$\text{flush peak pressure} = \max_{t_0 < t < t_c} P(t) \quad (4)$$

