7.2 PIVC- Insertion

Sonographic assessment and surface description of underlying anatomical features will be completed for lower arm cephalic veins on both arms to guide catheter insertion.

[figure not shown]

Figure 1. Vessel surface description based on ultrasound imaging. V, valve; T, termination; B, bifurcation; 1, insertion; dotted-line, vein path; arrow, direction of insertion.

Next, a PIVC will be inserted according to the Instructions For Use into the lower cephalic vein of one arm in accordance with a previously established standard operating procedure (see Appendix 16.2) of the participant by a trained phlebotomist or nurse using commercially approved devices with sonographic guidance. After successful cannulation a BD MaxZero™ needleless connector will be attached to the extension and flushed with 3-5 mL saline (0.9%, BD PosiFlush™; 306575; Becton Dickinson, USA), and site stabilized using a Tegaderm IV™ securement dressing²⁷.

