7.3 PIVC-blood collection and pressure monitoring

A Luer-Lok™ access device, connected to the needleless connector, and vacutainer tubes (2mL (waste tube), 2mL BD Vacutainer® EDTA, 1.8mg/ml-1, REF 367841; 6mL BD Vacutainer® EDTA, 1.8mg/ml-1, REF 367873; Becton Dickinson, USA; total volume: 10mL) will be utilized to collect blood and ascertain blood quality (haemolysis; see Appendix 16.3 for methodology). Prior to blood collection a pressure transducer (DTXPlus TNF-R, Cat. no. 682021; Argon Medical, USA) and flush syringe will then be connected to the needleless connector and zeroed against venous blood pressure. The catheter will be flushed while collecting pressure data in real-time with a custom-designed LabVIEW© routine. Thereafter, the extension set will be clamped and pressure transducer/flushing syringe disconnected from needleless connector.

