5.2.2.2 Blood draw fill time

It is hypothesized that:

- The blood draw duration observed for blood samples (all vacutainers, at all timepoints) collected from shorter catheters will be decreased when compared to longer catheters of the same gauge.
- The blood draw duration observed for blood samples (all vacutainers, at all timepoints) collected from smaller gauge (larger bore) catheters will be decreased when compared to larger gauge (smaller bore) catheters of the same length, over time.
- The blood draw duration observed for blood samples (all catheters, at all timepoints) collected into greater volume vacutainers will be increased when compared to smaller volume vacutainers.

A linear mixed effect model will be used with blood draw fill time as response and subject as random effect. Time, device configuration (gauge, length and their interaction), Vacutainer tube volume and baseline (at D1.2) blood draw fill time will be fixed effects. Contrast based multiple comparisons will be used to compare blood draw fill time between conditions (between gauge, between length) at each timepoint. Example tables for summary statistics (overall and per time point for each Vacutainer tube volume are given in the Appendix section by Table A.9.1 and Table A.9.2, respectively. Graphical representations of distribution of blood draw time per device is provided in Figure B.5.1 and of average blood draw time is shown in the Appendix section by Figure B.5.3. Example tables for ANOVA tables (Table A.9.3) and multiple comparisons (Table A.9.4) can be found in the Appendix A

5.2.2.3 Relationship between catheter blood draw patency indwell time and presence of intra/extravenous thrombi, thrombus length, thrombus type catheter angle/tip location *in situ*, catheter length in vessel, vein depth from skin surface, C/V ratio, and vessel anatomy

Relationship, if any, will be assessed through the computation of:

1. Summary statistics stratified by indwell time considered as a discrete variable (0, 6, 24, 30, 48, 54, 72 hours)
2. Scatter plot showing time between initial Thrombus observation to time of removal per Device Configuration
3. Bar plot showing percentage of thrombus for each time point per device configuration
4. Scatter plot showing thrombus length as a function of time grouped by device configuration
5. Relationship between flush technique and presence of Thrombus

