5.2.3.2 Flush pressure profile

Manual flush variability will be evaluated using duration of flush and characteristics of Flush pressure profile obtained on in-line pressure measurements. They will be comprised of:

- Peak pressure
- Flush duration (sec.)

For each of these characteristics, summary statistics by indwell time considered as a discrete variable (0, 6, 24, 30, 48, 54, 72 hours) and longitudinal line and bar plots will be generated on average for continuous and by proportion for categorical responses, respectively.

Lineplots will be similar to the example provided for cfHb in Figure B.3.2 and bar plots will be similar to the example provided for Haemolysis occurrence in Figure B.4.1, both represented in Appendix B.

Relationship between the occurrence of these events will be investigated using the Boruta algorithm with a survival random forest model (an example output from the algorithm is provided in the Appendix by Figure B.7.1) where the variables coding for these events will be predictors.

Based on the outcome of the Boruta algorithm, models might be used to investigate further the relationship between these variables and indwell time.

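### Flush duration is analysed in raw seconds although the measured flush may be 3 to 10 mL, so it cannot separate push rate from volume

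*SAP*

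**What the plan says.** SAP 5.1.7 states that the flush measures "will be derived from the pressure trace from a 3 to 10 mL saline flush performed upon first accessing the device at each time point". For Eq. 2, "the duration of the flush will be derived by subtracting time point zero from the completion time point". It adds an alternative: "the duration of the flush could be reduced to the time between the max pressure and the completion time point". The equation printed for that alternative (Eq. 3) is t_max - t_0. Peak pressure (Eq. 4) is the maximum pressure between t_0 and t_c.

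SAP 5.2.3.2 lists peak pressure and flush duration in seconds as the two flush characteristics. It summarises them by time point and uses them as predictors in a Boruta survival random forest, after which "models might be used to investigate further the relationship between these variables and indwell time". SAP 5.2.2.3 item 5 plans a further look: "Relationship between flush technique and presence of Thrombus". Technique is not defined there. The general covariates in SAP 5.2.4 are gender, age and BMI. No section fixes the flush volume, divides by it or adjusts for it.

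Protocol 7.3 describes the measured flush without a volume: "The catheter will be flushed while collecting pressure data in real-time". Protocol 7.2 has the catheter "flushed with 3-5 mL saline", but that is the flush after cannulation. Protocol Table 1 supplies a 10 mL pre-filled syringe. SAP 2.7 places the flush pressure profile at 7 time points and classes it as exploratory.

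**The concern.** The exploratory objective is to describe how manual flushing varies. Variation has at least two components: how much saline is pushed and how fast. Eq. 2 duration rises with the first and falls with the second. One number in seconds cannot show which of them moved.

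This matters most where duration becomes a predictor. Suppose the forest ranks duration as important for indwell time. The reader could not tell whether slow pushing, larger volumes or a mixture was associated with failure, and these would lead to different follow-up questions. The fault can also hide a signal, because a slow small flush and a fast large one may last equally long. The pressure trace as described does not yield volume, so a volume not noted at the bedside is lost to the analysis.

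**Working it through.** The documents give no planning figure for the flush endpoint, so there is nothing of theirs to reproduce.

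**Inputs from the documents.** Volume V from 3 to 10 mL (SAP 5.1.7); duration D = t_c - t_0 in seconds (SAP 5.1.7, 5.2.3.2); 7 time points (SAP 2.7); two catheters per participant. No push rates and no distribution of volumes are given, so those below are assumptions.

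**Step 1: range due to volume alone.** With mean push rate Q, D = V/Q. At equal Q the duration ratio equals the volume ratio: 10/3 = 3.33.

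| Assumed Q (mL/s) | D at 3 mL (s) | D at 10 mL (s) | Ratio |
|---|---|---|---|
| 0.5 | 6 | 20 | 3.33 |
| 1 | 3 | 10 | 3.33 |
| 2 | 1.5 | 5 | 3.33 |

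**Step 2: masking.** 3 mL at 0.5 mL/s takes 3/0.5 = 6 s. 10 mL at 1.67 mL/s takes 10/1.67 = 6 s. The durations are equal although the rates differ 3.3-fold.

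**Step 3: spread short of the extremes.** If V were uniform on 3 to 10 mL and Q constant, the coefficient of variation of D would be (7/√12)/6.5 = 31%. An even mix of 3 and 10 mL gives 3.5/6.5 = 54%. If the range were only 3 to 5 mL, it would be (2/√12)/4 = 14%, with a maximum ratio of 5/3 = 1.67.

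**Step 4: share of variance.** log D = log V - log Q. With V uniform on 3 to 10 mL, the SD of log V is 0.335 (variance 0.1125). If V and Q are independent, volume's share of the variance of log D is 0.1125/(0.1125 + s²), where s is the SD of log Q.

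| Assumed s | Share due to volume |
|---|---|
| 0.1 | 92% |
| 0.2 | 74% |
| 0.3 | 56% |
| 0.5 | 31% |

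**Step 5: after the change.** At equal rate, D/V is the same for 3 mL and 10 mL (at 1 mL/s, 3/3 = 10/10 = 1.0 s/mL), so the ratio falls from 3.33 to 1.00.

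**Step 6: extent.** Up to 7 × 2 = 14 measured flushes per participant are affected.

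**Step 7: the other flush measures.** Eq. 4 is a maximum and does not scale with volume by construction. Eq. 3 as printed is the time from start to peak and need not scale with volume. The accompanying words describe the time from peak to completion, which could. Which version is meant therefore decides whether the alternative has the same weakness.

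**The case against.** The strongest reply is that little hangs on this. The endpoint is exploratory, the study is a feasibility study with no acceptance criteria, and no flush hypothesis is stated. Follow-on models are optional. Flush duration is not a covariate in the primary Cox model, nor among the exploratory variables listed for the Boruta analysis in SAP 5.2.2.3. The preliminary business analysis in SAP 2.6 takes items 1, 2, 3, 4 and 7 of that section, and so leaves out item 5; it also leaves out 5.2.3.2. All of this stands and limits the weight of the point.

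It can also be said that the volume an operator gives is part of manual variability. That is fair, but it argues for showing volume separately from speed, which raw seconds cannot do. The flush CRF is not among the documents and may already capture volume; the SAP as written still would not use it.

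A reader might infer more than the documents support:

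- That all flush findings are compromised. Peak pressure is a co-equal measure and is not affected by construction.
- That duration was meant as a measure of catheter resistance. The documents name manual flush variability and never resistance.
- That flush volume differs by device or arm, or with a failing catheter, and so biases the device comparison. Nothing shows this. The inserter and study manager know the device, but the documents do not say that either performs the session flush.
- That the 3-5 mL in Protocol 7.2 contradicts SAP 5.1.7. These are different flushes. The gap is that Protocol 7.3 is silent on the measured one.

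**Conclusion.** The point holds for Eq. 2 duration. With 3 to 10 mL permitted and no volume term, duration mixes volume with push rate by up to 3.33-fold at equal rate. That figure is the extreme pair and not an estimate of actual confounding. The variance shares rest on an assumed uniform volume, independence of volume and rate, and assumed rate variability. If practice settled on one volume, the problem would largely vanish. If volume varies at random, the certain effect is added noise in an exploratory predictor; bias between devices is possible but not shown. The primary indwell-time analysis does not use this variable. This is an inexpensive improvement to an exploratory variable and casts no doubt on the main comparison.

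**What to change.** 1. Record the delivered volume with each measured flush, for example from the syringe graduation before and after, unless the flush CRF already does so.
2. In SAP 5.1.7 and 5.2.3.2, analyse duration per mL, or mean flow rate V/(t_c - t_0), or include volume as a covariate. Do the same in 5.2.2.3 item 5 if duration is used there. For the Boruta step the rate variable, with volume as its own feature, is cleaner: raw duration entered beside volume could still rank as important because of volume. In regression models a volume covariate also avoids assuming strict proportionality.
3. Tabulate delivered volume by device configuration.
4. State the session flush volume consistently in Protocol 7.3, which gives none, and SAP 5.1.7. The value is for the sponsor and investigator.
5. Reconcile the alternative duration in SAP 5.1.7: the text runs from maximum pressure to completion, while Eq. 3 is t_max - t_0.

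The cost is at most one data field, a few seconds per flush to read the syringe, one derived variable and some wording. No extra procedure is needed.
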